## Study Design and Methods

Subjects will be recruited and randomized into two groups using a random block method at the end of the baseline visit. One group will receive the FES intervention and the other group will continue with their activities of daily living. The study consists of a baseline visit and four follow up visits at 4 weeks, 8 weeks, 12 weeks and one final visit three months from the 12 week visit or from the discontinuation of the FES. Outcome measures will be taken for both groups during these visits. Each visit is expected to take no more than two hours.

Following informed consent, it will be verified and documented that participants meet the inclusion/exclusion criteria. Most of the inclusion/exclusion criteria are self report, with the exception of the monofilament evaluation and the evaluation of voluntary muscle contraction. An investigator will administer the tests. For the sensory testing the participant will be asked to close their eyes and inform the investigator when they sense the pressure of the monofilament on their LE. In order to continue with the study procedures, the participant must be able to feel a minimum of 7 of the 10 areas tested. Participants will also be evaluated to determine if a voluntary muscle contraction is present. To do this the FES electrode pads will be placed on the participant and the investigator must be able to observe a muscle contraction in order to proceed. Any participants who do not meet the inclusion/exclusion criteria for the study will be withdrawn.

The following procedures and outcome measures will be obtained from a blinded (second) assessor at the baseline visit.

1. Residual knee extension strength will be tested using a standardized Biodex protocol and a custom attachment (System 3, Biodex Medical Systems, NY). The participant will practice first on the biodex machine with their intact limb.

2. The residual limb volume will be measured with the use of a hand held three-dimensional motion-tracking laser scanner system. Reflective markers will be placed on a sock over the residual limb located at the tibial tubercle, fibular head, and anterior distal tibia. Circumferential measurements of the residual limb will be taken with a tape measure. Longitudinal measurements of the residual limb will be taken with a straight ruler. Using a standard scale, participant's height and weight will be recorded.

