follow: lag delay of 3 seconds, ramp up time of 2 seconds, on time of 9 seconds and ramp down of 1 second. For the smaller muscles of the gastroc/soleus and anterior tibialis muscles we will start with the setting of the 300ms pulse width and 35 Hz for the pulse rate. There will be no lag delay. Channel 1 settings will be as follows: ramp up time of 2 seconds, on time of 10 seconds and ramp down time of 2 seconds. Channel 2 settings will be as follows: ramp up time of 2 seconds, time on of 10 seconds and a ramp down for 2 seconds. The pulse rate and width will be increased at each visit per participant's comfort level.

We will record the settings at each visit and instruct the patient to not change the settings. The Continuum device locks the intensity increase buttons to prevent accidental increases in intensity. This safety feature is activated after 20 seconds of unchanged intensity.

Both study groups will be given daily logs to record daily prosthetic wearing times, changes in health, medications, activity, pain levels and FES use (the intervention group only).

Intervention group participants will be directed to use the FES for 15 contractions per muscle group (totally approximately 45 minutes) a minimum of three times per week for the next three months at home. We will set up a face-to-face visit with the FES participants at the end of the first week and call the FES participants every two weeks thereafter to check on compliance and address any issues with using the device. If the participant reports an ill-fitting prosthesis during the study, we will refer the participant to their local prosthetist for proper adjustments. If the prosthetic socket warrants replacement, the participant will be withdrawn from the FES intervention, we will perform the above mentioned outcome measures and continue to follow them until the 3 month final follow up visit.

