## **Statistical Plan**

Descriptive statistics will be computed and variables will be assessed for normality. Nonparametric tests will be performed in the event the data are not normal. An unpaired t-test or chi-square test depending on the type of variable will be used to compare the subject demographic variables (e.g. age, level of amputation, gender, etc.) between groups. A mixed model repeated measures ANOVA will be used to compare the outcome measures between groups and overtime. Compliance with the FES (e.g. average number of hours of use per week) will be entered as a covariate. We will also use correlation statistics (Pearson or Spearman) to examine the relationship between amount of FES used and changes in the dependent variables. Should significant main and interaction effect differences be found ( $p < 0.05$ ), post-hoc analyses will be used to examine the differences in variables across the groups and time points. If the data fail to be normally distributed the Friedman test will be run.

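### FES compliance, a post-randomisation variable that is zero or undefined in every control, is a covariate in the only between-group outcome model and can distort the group main effect

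*Combined protocol and SAP*

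**What the plan says.** The Statistical Plan gives one model for comparing the groups on the outcomes: "A mixed model repeated measures ANOVA will be used to compare the outcome measures between groups and overtime". The next sentence adds the covariate: "Compliance with the FES (e.g. average number of hours of use per week) will be entered as a covariate". The plan does not say what value controls take, whether compliance is centred, or whether it enters as one value per person, by visit, or crossed with time. It states no covariate-free version of this model. Follow-up comparisons are conditional: "Should significant main and interaction effect differences be found", at the 0.05 level, post-hoc analyses follow. Separately, Pearson or Spearman correlations are planned "to examine the relationship between amount of FES used and changes in the dependent variables".

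Study Design and Methods shows where compliance data come from. Randomisation is at the end of the baseline visit. One group receives FES and "the other group will continue with their activities of daily living". Both groups keep daily logs, but device use is an entry for one arm: "pain levels and FES use (the intervention group only". The FES arm is told to use the device "a minimum of three times per week for the next three months at home", and staff "call the FES participants every two weeks thereafter to check on compliance". Controls may be offered FES only after the study ends, if it proves beneficial.

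**The concern.** Hours of FES use are a consequence of assignment, and within the FES arm they depend on who the participant is. Putting them in the model that estimates the effect of assignment changes what the group term means. With controls at 0, the group coefficient compares FES participants at zero hours with controls. The trial does not ask that question: its objective is whether at-home use brings benefit.

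Three things can follow. If benefit runs through hours of use, the covariate takes it and the group term is left near zero. If people who use the device more would have done better or worse anyway, the group term is biased, in a direction that cannot be known beforehand. If neither holds, the group term is unbiased but less precise. If controls are instead left missing, a complete-case fit drops the whole control arm and no comparison remains.

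A working device could therefore show no group main effect, and an inert one could show a spurious effect. Because the coding is unstated, it could also be settled after the results are seen.

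**Working it through.** **Inputs.** The documents give the model, the covariate, the timing of randomisation, the arm in which use is recorded, five visits (baseline, 4, 8 and 12 weeks, and three months later) and the 0.05 level. They give no sample size, power, effect size, SD, allocation ratio or spread of use, so there is no plan figure to reproduce. Assumed here: 1:1 arms of n = 20 for the simulations, two-sided testing, outcome SD 1, within-person correlation 0.7, one compliance value per person, and controls coded 0. Let c be the coefficient of variation (SD/mean) of use in the FES arm. For scale, the prescribed minimum is 45 min × 3 / 60 = 2.25 hours per week, so if that were the mean, c = 0.5 would be an SD of about 1.1 hours.

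**What the group term becomes.** Controls do not vary in use, so the compliance slope b is estimated from the FES arm alone. The group coefficient is (FES mean) − b × (mean hours) − (control mean), the contrast at zero hours.

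**Precision.** Without the covariate, the variance of the group effect is 2σ²/n. With it, the variance is (σ²/n)(2 + 1/c²). The standard error is multiplied by √(1 + 1/(2c²)). At c = 0.25 this is √(1 + 8) = 3.0. Nominal 80% two-sided power corresponds to a standardised effect of 1.96 + 0.84 = 2.80, which is divided by the same factor.

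**Absorption.** Suppose benefit is 0.7 SD at each of the four follow-up visits, so the five-visit main effect is 0.7 × 4/5 = 0.56. If benefit is proportional to hours and use is unrelated to prognosis, b × (mean hours) equals the whole 0.56 and the group term is estimated at about 0 for every c.

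**Bias.** If use correlates r with the person's underlying level, the group term is shifted by −r√0.7/c. At r = 0.5 and c = 0.25 this is −0.5 × 0.837/0.25 = −1.67.

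| c | SE multiplier | Power, from 80% | True 0.56 independent of hours, r = +0.5 | Same, r = −0.5 | False positives, no effect, r = ±0.5 |
|---|---|---|---|---|---|
| 0.25 | 3.0 | 15% | −1.1 | 2.25 | about 52% |
| 0.50 | 1.7 | 37% | −0.3 | 1.4 | about 42% |
| 0.75 | 1.4 | 53% | 0.0 | 1.1 | about 31% |
| 1.00 | 1.2 | 63% | 0.15 | 1.0 | about 23% |

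The last three columns are simulated. Without the covariate the false-positive rate is about 5%. At a weaker r = 0.2 it is still about 8% to 11%.

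**Group-by-time at week 12.** The answer depends on how compliance enters, for a true benefit of 0.70 SD proportional to hours:

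- One value per person, main effect only: the covariate cancels from within-person change. The SE ratio is 1.00 and the estimate is about 0.70, so there is no damage.
- Crossed with time: SE ratios are 3.1, 1.8, 1.4 and 1.2 across the four values of c, and the estimate is about 0.
- Entered by visit (0 at baseline and at the final visit): SE ratios are 2.1, 1.3, 1.2 and 1.1. The estimate is 0.28 to 0.30 if benefit persists to the final visit, or about 0 if it ends when the device is returned.

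**Other codings.** Centring compliance within the FES arm with controls at 0 reproduces the group estimate of the model without the covariate. Coding controls as missing leaves no controls in a complete-case fit, and the group effect cannot be estimated.

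**The case against.** The strongest reply is that the contrast the trial most needs survives. The covariate reads most naturally as one average per person, and entered once it leaves group-by-time alone. Hypothesis 4 asks for greater improvement from baseline than in controls, which is group-by-time, and Hypotheses 1 to 3 are also worded as changes. The tabulated figures concern a main effect averaged over five visits, one of which precedes randomisation. This stands as a limit on the damage. It does not clear the plan, because the plan tests main effects as well as interactions, makes post-hoc comparisons depend on both, and does not rule out the forms that damage group-by-time.

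It is also fair that every size rests on assumed inputs, and that the bias is proportional to r: with r = 0 and a constant benefit there is no bias, only lost precision. Equally, the near-zero estimate under proportional benefit requires r = 0; with r = ±0.5 the prognosis bias is added to it.

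The plan does mention post-hoc analyses and unnamed nonparametric tests without naming a covariate. The first depend on the model in question. The one nonparametric test named for repeated outcomes, Friedman's, is a within-person test that does not compare independent groups. A fit that lost every control would fail visibly, so that branch is the least likely to mislead.

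**Conclusion.** The concern holds and should be fixed before analysis. Compliance is post-randomisation, has no meaningful value in controls, and enters the only named between-group outcome model with no stated coding. With controls at 0 and one value per person, the group main effect is no longer the effect of assignment to FES. Depending on how use relates to benefit and prognosis, it is removed (0.56 SD estimated at about 0), shifted in either direction (0.56 estimated anywhere from −1.1 to 2.25 for r = ±0.5), or estimated with a standard error 1.2 to 3.0 times larger. These sizes assume 1:1 arms, c between 0.25 and 1.0 and within-person correlation 0.7; they illustrate the range and do not predict this trial's result. The group-by-time contrast is safe only under a specification that the plan leaves unstated. A larger sample would recover precision but would not remove the bias or the absorption.

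**What to change.** Replace the covariate sentence in the Statistical Plan with:

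> The mixed model will include group, visit and group-by-visit. All randomised participants will be analysed by assigned group. FES compliance will not be a covariate in this model.

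Then add to the sentence on Pearson and Spearman correlations:

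> This dose-response analysis is exploratory and uses FES-group participants only.

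The question about amount of use is kept, since the correlations already address it. The cost is four short sentences in place of one, with no new data, visits or participants.

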Most studies on FES have shown positive results when combining FES with activity (e.g. knee flexion/extension exercises, cycling etc.) (9). It is difficult to exercise a muscle that has been amputated and is partially intact. FES conditions the muscle similar to exercise. Our clinical experience has found improvements in knee function, socket fit, and reductions in pain with wearing FES alone. With this study, one of the main functional outcomes that we are investigating is knee extension. We plan to place the FES electrodes on the medial and lateral quadriceps muscles in hope to show positive changes in muscle strength and volume. The gastroc/ soleus and tibialis anterior muscles have been amputated and have a secondary insertion point, therefore they are difficult to strengthen by exercising. We would like to investigate the effects of the FES on these two muscles in hopes to decrease atrophy or increase muscle volume. Should we demonstrate that FES alone helps improve the outcome measures in this study; it could potentially be a highly practical, easy to use, cost effective treatment that can be done at home.

**Objective:** To determine if at-home FES use without prosthetic wear results in benefits to persons with unilateral, trans-tibial amputations (TTA) who are at least two years status post their amputation surgery.

Hypothesis 1: FES will increase knee extension strength in the residual limb

Hypothesis 2: FES will increase volume of the residual limb

Hypothesis 3: FES will decrease chronic and phantom pain of the residual limb

Hypothesis 4: In comparison to the control group, FES training will show greater increases in velocity, step length, and percentage in stance time on the amputated limb after training when compared to baseline as measured using the GaitRite System.

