At each follow up visit the log book entries will be collected and reviewed. A second investigator will inspect the residual limb and check the fit of the prosthetic socket, record residual limb knee extension strength on the Biodex machine, take anthropometric measurements (circumferences and lengths) of the residual limb with a tape measure and ruler, and scan the limb with the hand held three-dimensional motion-tracking laser scanner system. The participant will be asked to complete the pain questionnaire at all four followup visits and the Prosthetic Evaluation Questionnaire (PEQ) at the 12 weeks and 3 month followup visits.

For the isokinetic evaluation with the Biodex, the individuals will be positioned in the dynamometer, sitting with the trunk, pelvis and thigh stabilized by belts. The back of the chair will be inclined at an 85 degree angle and the rotational axis of the device will be aligned with the rotational axis of the knee joint, at the level of the lateral epicondyle of the femur. The lever arm was positioned parallel to the leg, with the support cushion modified for the amputee and positioned at the mid-calf. The test will be performed in a total range of motion of 110 degrees. The knees will be positioned in 60 degrees of flexion to start.

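### If normality fails, the only test named for the repeated outcomes (Friedman) ignores the randomised arm, so no FES-versus-control test is prespecified

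*Combined protocol and SAP*

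**What the plan says.** The trial has two randomised arms: "Subjects will be recruited and randomized into two groups using a random block method at the end of the baseline visit". Study Design and Methods sets a baseline visit and four follow-up visits. Most outcomes can therefore have five time points. The quality-of-life questionnaire has three: baseline, then "the Prosthetic Evaluation Questionnaire (PEQ) at the 12 weeks and 3 month followup visits".

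The Statistical Plan gives the main analysis as follows: "A mixed model repeated measures ANOVA will be used to compare the outcome measures between groups and overtime". For non-normal data it has two sentences. The first is general: "Nonparametric tests will be performed in the event the data are not normal". The second, which ends the section, names a test: "If the data fail to be normally distributed the Friedman test will be run".

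Of the four hypotheses under the Objective in Background, the fourth is explicitly a comparison of arms: "In comparison to the control group, FES training will show greater increases in velocity, step length". Hypotheses 1 to 3 state a direction of change under FES and do not mention control, but the mixed-model sentence plans a group comparison for the outcomes without exception.

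**The concern.** Friedman is a one-way within-subject test. It asks whether the visits differ from one another within participants. It has no between-subject factor, so it cannot estimate or test the difference between FES and control.

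An analyst who follows the plan literally on non-normal data would report a time effect and no randomised comparison. One who departs from it would choose a between-group test after seeing the data. In the first case, a trend shared by both arms can be reported as significant. Practice on repeated maximal strength tests could cause one, as could regression to the mean in participants who must have chronic limb pain to enter. A real FES effect could not be attributed to FES.

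**Working it through.** The plan states no sample size, SD, effect size or dropout rate, so there is no figure of its own to reproduce. The check has four parts. The first two need no assumed effect sizes.

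**1. Which named method uses the arm?**

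| Method in the Statistical Plan | Applied to | Compares arms on outcomes? |
|---|---|---|
| Mixed model repeated measures ANOVA | Outcomes | Yes |
| Unpaired t-test or chi-square | Demographics | No |
| Pearson or Spearman | Amount of FES use against change | No |
| Post-hoc analyses | After significant main and interaction effects | Yes, but no test is named, and Friedman yields no group or interaction effect to trigger them |
| Nonparametric tests, general sentence | Non-normal data | Not specified |
| Friedman | Non-normal data | No |

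The Spearman option does not fill the gap, because its stated use is a dose-response question: "We will also use correlation statistics (Pearson or Spearman) to examine the relationship between amount of FES used and changes in the dependent variables".

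**2. What the Friedman statistic contains.** Let N be the participants in both arms together, k the number of visits, and R_j the sum over participants of the within-participant rank of visit j. Then

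Q = 12 / [N k (k+1)] × Σ R_j² − 3N(k+1).

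With k = 5 this is Q = 0.4 × Σ R_j² / N − 18N. No term carries the arm. Two extreme cases with equal arms:

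- Every FES participant rises at each visit and every control falls at each visit. R_j = (N/2)j + (N/2)(6 − j) = 3N, so Σ R_j² = 5 × 9N² = 45N² and Q = 18N − 18N = 0.
- Every participant in both arms rises at each visit. R_j = jN, so Σ R_j² = 55N² and Q = 22N − 18N = 4N, its maximum, N(k − 1).

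Complete separation of the arms gives zero, and identical arms give the maximum. In one simulated data set, shuffling the arm labels left the result unchanged (statistic 13.36, p = 0.0096 both times).

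**3. Size under assumed inputs.** The assumptions are compound symmetry, normal errors, five visits, drift at 0, 1/3, 2/3, 1 and 1 of its maximum, two-sided 0.05, and 4,000 runs per setting. The table gives rejection rates.

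| Scenario and test | 15/arm, ρ 0.6 | 15/arm, ρ 0.8 | 20/arm, ρ 0.6 | 20/arm, ρ 0.8 |
|---|---|---|---|---|
| No FES effect, no drift: Friedman | .041 | .046 | .048 | .054 |
| No FES effect, shared drift 0.1 SD: Friedman | .071 | .091 | .071 | .122 |
| No FES effect, shared drift 0.2 SD: Friedman | .151 | .281 | .184 | .360 |
| No FES effect, shared drift 0.3 SD: Friedman | .311 | .588 | .411 | .736 |
| Arms move +0.4 and −0.4 SD: Friedman | .035 | .027 | .040 | .029 |
| Same: rank ANCOVA | .690 | .886 | .822 | .962 |
| Only FES moves, +0.8 SD: Friedman | .457 | .745 | .597 | .877 |
| Same: rank ANCOVA | .693 | .883 | .834 | .964 |

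Over the no-effect settings, rank ANCOVA rejects .046–.057 and Mann-Whitney on week-12 change .043–.052. With 10–30 per arm, the Friedman range at 0.3 SD shared drift widens to .192–.914. With three time points, as for the questionnaire, it is .344–.728 at 15–20 per arm.

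The fallback applies to non-normal data, so the same design was repeated with skewed (exponential) participant and error terms. Friedman then rejects 11–25%, 34–76% and 64–97% at shared drifts of 0.1, 0.2 and 0.3 SD.

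**4. Two further checks.** *Friedman run separately by arm.* With no FES effect, both arms have the same rejection probability π, so a result significant in FES but not in control has probability π(1 − π), at most 0.25. With skewed data and a shared shift of 0.8 units (participant and error SD 1 each; 3,000 runs):

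| Per arm | π | π(1 − π) | Simulated |
|---|---|---|---|
| 10 | .514 | .250 | .256 |
| 15 | .735 | .195 | .200 |
| 20 | .857 | .123 | .122 |
| 30 | .972 | .027 | .032 |

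In the normal-error settings at 0.3 SD drift, the pattern appears in .138–.250.

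*Complete visits.* Standard Friedman uses only participants with every visit. At an assumed 5% or 10% missing per follow-up visit, independently, 0.95⁴ = .815 or 0.9⁴ = .656 remain for five-visit outcomes, and 0.95² = .903 or 0.9² = .81 for the questionnaire.

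**The case against.** The strongest reply is that the Friedman sentence does not say which analysis it replaces. It may cover only the over-time question, with the general sentence leaving room for a rank-sum test between arms. On that reading the plan has an unspecified between-group fallback, not a decision to drop the comparison. That reading is possible, but it does not rescue the plan: the general sentence names no test, outcome or time point, so on either reading no arm comparison is fixed in advance.

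Several limits do stand. The branch is conditional, and nothing in the documents shows how often it would be reached. Hypotheses 1 to 3 are not worded against control. The simulation inputs are all assumed, and the table uses normal errors for a branch defined by non-normality, although skewed errors raise the false-positive rates. If only FES improves, Friedman does often reject, but it still cannot say which arm changed. For a missed last visit the protocol plans a visit or a phone interview, which would reduce missing data, though a phone call cannot supply strength, volume or gait.

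Nor is the mixed-model branch free of questions. The plan states: "Compliance with the FES (e.g. average number of hours of use per week) will be entered as a covariate", while FES use is logged in the intervention arm only. That is a separate point and does not alter this one.

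**Conclusion.** The concern holds. The named fallback cannot make the comparison that randomisation supports and Hypothesis 4 requires, and no other sentence prespecifies a test that can. This follows from the definition of the statistic and rests on no assumed figure.

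The practical size does rest on assumptions. At 15–20 per arm with a shared drift of 0.1 to 0.3 SD and no FES effect, pooled Friedman rejects in 7% to 74% of trials with normal errors and 11% to 97% with skewed errors. The 3–4% rejection under opposite trends is a worst case. The defect is confined to the non-normal branch. It should be fixed before analysis, but it does not undermine the whole plan.

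**What to change.** Replace the Friedman sentence with one prespecified between-group fallback, stating:

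- **Test.** Either rank ANCOVA of the follow-up value on baseline with arm as the factor, or a permutation test of the mixed model's group-by-time contrast. The second keeps all visits. If it is chosen, say whether the compliance covariate stays in the model.
- **Time point or contrast.** Week 12, the end of treatment, is a natural choice, but the documents make no visit primary, so the sponsor must state it.
- **Trigger.** A named check on the mixed-model residuals. The plan does not currently say whether normality is judged on raw data or residuals, or by what criterion.
- **Role of Friedman.** If kept, a descriptive within-arm summary only, with no inference from significance in one arm and not the other.

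The cost is wording in the Statistical Plan; no new data are needed. A rank method used when the data are in fact normal should lose a little power, which was not calculated here. A single-visit rank ANCOVA also sets aside the other follow-up visits.
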